Protocol Title: Validating Low FDG Dose PET/CT compared to current Standard of

Care Dose PET/CT

Protocol Project Number: RP0308

Protocol Date: May 22, 2017

Principal Investigators:

[name], PhD

Vice Chairman and Professor, Department of Radiology

Novartis Chair of Imaging Research

The Ohio State University

[name]

[name]

[contact]

[contact]

E-Mail: [contact]

[name], DABR

Assistant Professor of Radiology

Diagnostic Medical Physicist

[name]

[name]

[contact]

[contact]

E-Mail: [contact]

I. Overview

Positron Emission Tomography/Computed Tomography (PET/CT) imaging using ¹⁸F-FDG is an important, commonly used cancer, neuroscience and cardio-vascular imaging methodology to detect disease and to monitor therapeutic interventions. While considerable technological progress of PET/CT systems has occurred over the last decade, we have not re-evaluated the ability to potentially reduce the radiation burden of the used PET imaging pharmaceutical (FDG).

This early phase trial intends to accomplish the following:

- to validate that the radiation dose burden from the PET imaging pharmaceutical (FDG) can be reduced by more than 50% from the current standard of clinical care (SOC) level without affecting the diagnostic ability;
- to confirm that a low dose approach will be feasible for response assessment;
- to validate that the difference in FDG uptake between imaging 60 min +/- 10 min post injection and 75 min +/- 10 min post injection is independent/equivalent of the injected FDG dose
- to validate a simulation methodology to streamline future dose finding studies for PET imaging pharmaceuticals.

II. Objectives

Aim 1: To validate equivalency of low dose FDG PET/CT (185 MBq [5 mCi]) compared to current standard of care FDG PET/CT dosing (481 MBq [13 mCi]).

Aim 2: To validate that the difference in FDG uptake between imaging 60 min post injection and 75 min post injection is independent/equivalent of the injected FDG dose

Aim 3: To validate equivalency of simulated FDG dose PET/CT images to effective dose reduced FDG PET/CT images

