For secondary assessments, we will determine by three independent, blinded readers the image quality for a diagnostic interpretation with a linear 10 cm scale from exceptional to unacceptable. We will use the same approach to assess the diagnostic confidence and occurrence of image artifacts and to allow for any additional comments desired. For the read assessment, each PET/CT exam will be individually assessed in a randomized order. Upon completion of this assessment and after a duration of several weeks, a matched pair assessment will be performed to assess equivalency during a side-by-side comparison using the same assessment scales. If those assessments confirm equivalency, we plan to add a full diagnostic read of each exam separately with blinded dosing information.

For this Phase I study, we believe that performing intra-individual comparisons on the same PET/CT system is the only way to get unconfounded, objective assessment of the equivalency of dose reduction. In case we would find difference between the four different PET/CT systems, different dose reduction schemes might be necessary.

While we cannot evaluate in this trial the equivalency for response assessment of therapy between the low dose and current standard of care dose, we do have at least the ability to evaluate that the difference in FDG uptake between the whole body sweep at 60 min +/- 10 min and 75 min +/- 10 min for the target regions is not impacted by dose. While this is our hypothesis we want to evaluate, we will at the same time gain insight into the intra-individual variability in FDG uptake within such a 15 min +/- 10 min window. The current guidelines recommend that the PET/CT whole body sweep be performed 60 min +/- 10 min post injection, giving a 20 min window to start the whole body sweep [Shankar]. Current clinical practice however is favoring imaging around 75 min p.i. which leads to a considerable number of protocol deviations in clinical trials.

As Imaging Core Laboratory for a large number of trials which include PET imaging, we see that the protocol deviation rate in time post injection is consistently the highest with rates of 15% to 40% depending on protocol, most frequently however in the time frame of 70 to 80 min post injection. By adding this aim to the protocol, we can answer another burning clinical/scientific question without adding any additional radiation exposure to the patient.

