If the lower dose PET/CT examination is determined to be equivalent to the current standard of care, we will change our standard of care and follow-up examinations maybe performed at lower dose levels.

Safety Monitoring:

The safety of data and patients will be managed consistent with the clinical protocols in place for PET imaging at The Ohio State University Wexner Medical Center. The difference compared to standard of care scans is solely in the fact that we are using a substantially lower dose of PET radiotracer compared to the current standard. All other safety aspects are equivalent.

As part of the standard of care imaging procedure, safety monitoring is in place for patients. This will include the monitoring of the physiologic parameters that are deemed appropriate in the evaluation of potential risk during the acquisition process (electrocardiogram, respiration rate, core body temperature). These parameters are monitored to ensure that they do not approach potentially hazardous levels. The Principal Investigators or Co-Investigators are able to respond immediately to ensure the safety of the patients participating in the research study. The Principal and/or Co-Investigators or Key Personnel will be present at the time of all non-standard of care PET acquisitions to ensure this.

Patient participation maximum duration and frequency is defined by protocol as follows: Duration of data acquisition in the PET system per patient is limited to no more than 2 hours total per day consisting of one or more acquisitions.

In the event of any medical emergency, accident or trauma while the subject is in the laboratory, our contingency plans for emergency situations are as they would be for any medical facility and clinical magnetic resonance imaging facility. Our emergency protocol fully prepares us to provide access to emergency treatment for our patients, resuscitation, life support and medical care as needed.

Confidentiality of Records:

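### The separate diagnostic read, the only planned comparison of what is found at each dose, comes after the side-by-side session and depends on its result; it should come first

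*Protocol*

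**What the plan says.** In the protocol's Overview, the first listed intention is to show that the FDG radiation burden "can be reduced by more than 50% from the current standard of clinical care (SOC) level without affecting the diagnostic ability".

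The primary endpoint is SUVmax. The secondary reader assessments are set out in Measurement / Instrumentation, in this order:

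1. Individual scoring. The text reads "we will determine by three independent, blinded readers the image quality for a diagnostic interpretation with a linear 10 cm scale", and adds "We will use the same approach to assess the diagnostic confidence and occurrence of image artifacts". The exams are kept apart at this step: "For the read assessment, each PET/CT exam will be individually assessed in a randomized order".
2. Paired viewing. After an interval of several weeks, "a matched pair assessment will be performed to assess equivalency during a side-by-side comparison using the same assessment scales".
3. Diagnostic read. "If those assessments confirm equivalency, we plan to add a full diagnostic read of each exam separately with blinded dosing information".

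No second reader panel is named, and no interval is given between steps 2 and 3. The Benefits paragraph under Detailed study procedures says what follows from a positive result: "If the lower dose PET/CT examination is determined to be equivalent to the current standard of care, we will change our standard of care".

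**The concern.** A separate, dose-blinded read of each exam is useful because what is reported on one exam does not draw on the other. Step 3 is placed where that independence is hardest to keep, since it follows a session in which a patient's two exams are displayed together. Blinding the reader to dose does not remove memory of a lesion.

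In a trial that seeks equivalence, an error that makes the two arms look alike works in favour of the conclusion sought. It is also hard to undo: once readers have seen the pairs, those readers can no longer give a read that is free of them.

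The condition on step 3 raises a second, smaller matter. Where steps 1 and 2 do not confirm equivalence, no comparison of findings is planned. Yet lower quality or confidence scores need not mean missed lesions, and similar scores need not mean the same findings.

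**Working it through.** The point rests on the order of the steps, so the check is mainly a reading of the protocol's statements against one another.

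**Which assessments compare findings between doses?**

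- SUVmax (primary; Measurement / Instrumentation and Data Analysis) compares uptake values in regions of interest. It does not compare what a reader detects.
- Image quality, diagnostic confidence and artifacts (steps 1 and 2) are ratings on a scale. A reader can be confident and still miss a lesion.
- The clinical read covers the standard-dose exam only. Research Design reserves the investigational exam for research evaluation.
- The full diagnostic read (step 3) is the only assessment in which what is reported at one dose can be set against what is reported at the other.

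**What protects each step from carry-over?**

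- Step 1: exams assessed singly, in randomized order.
- Step 2: an interval of several weeks after step 1.
- Step 3: exams read separately and blinded to dose. No interval and no new readers are stated.

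The protocol thus guards against memory between steps 1 and 2, and states no such guard between steps 2 and 3.

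**Direction of the bias if the same readers do step 3.** Let m be the share of lesions reported at standard dose that an independent low-dose read would miss. Let r be the share of those misses that the reader reports after all, from memory of the paired session.

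- Apparent miss rate = m × (1 − r)
- Bias = m × (1 − r) − m = −m × r

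As r runs from 0 to 1, the apparent miss rate runs from m (no bias) to 0 (the loss fully hidden). By this mechanism the bias is never in the other direction. The same algebra holds for lesions seen at low dose and missed at standard dose, so both kinds of disagreement shrink. The protocol gives neither m nor r, so the direction can be stated but not the size.

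**The plan's own sample size, as background.** Inputs from Sample Size Considerations: coefficient of variation 12%, limit 10%, alpha 0.025 per one-sided test, two-period crossover. With within-subject SD 0.12, standard error 0.12 × √(2/n), limits ±0.10, true difference 0 and n − 2 degrees of freedom, n = 33 gives power 0.813, and 33 is the smallest n that reaches 80%. Allowing for 10% drop-out, 33 / 0.90 = 36.7, rounded up to 37. Both stated figures reproduce. They size the SUVmax test and say nothing about the precision of the diagnostic read.

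**The case against.** The strongest reply is that recall bias is inferred from silence. The protocol does not say that the same three readers perform step 3 or that it follows at once. Reader assignment and intervals for an added read are often left to a reader charter or the SAP. Some delay is also implied, because step 3 waits until equivalence is confirmed; if that means the sub-study's own tests, the reads must first be completed and analysed. A reader would then have to remember lesions across 66 to 74 exams per sub-study (33 × 2 to 37 × 2). This stands as a limit on certainty. It does not remove the point, because the order of the steps is stated, and the order creates the exposure.

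Three stronger readings are tempting, and the protocol does not support them:

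- *Diagnostic ability is measured with bias or not at all.* Image quality for diagnostic interpretation and diagnostic confidence are scored for every exam, without condition, before any pair is shown. They are subjective and do not compare findings, but they are not nothing.
- *The condition on step 3 manufactures a false claim for the low dose.* Where equivalence is not confirmed, the Benefits paragraph triggers no change of practice, and Research Design already foresees further testing. Skipping the read there loses information; it cannot by itself create a false claim.
- *The change of standard of care will rest on a biased read.* The Benefits paragraph refers to the low-dose exam being found equivalent and does not mention the diagnostic read. The primary endpoint is SUVmax, and the reader outcomes are secondary.

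**Conclusion.** The point holds as a weakness of reading order. The only planned comparison of findings between doses is placed after the session most likely to compromise its independence, and is made conditional on that session's result. Whether bias occurs depends on the same readers performing step 3, which is likely, since only one panel is named, but is not stated. If they do, the bias is toward agreement and so toward equivalence. Its size is unknown: it could be negligible if the delay is long and recall is poor.

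The change is worth making because the comparison bears directly on the first aim in the Overview and the remedy uses the same images and readers. It does not put the primary SUVmax analysis in doubt. It should be settled before paired reading begins.

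**What to change.** In Measurement / Instrumentation, change the reading order as follows:

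- Do the full diagnostic read of each exam in the first session, in which exams are already assessed singly, in randomized order and blinded.
- Within that session, keep a patient's two exams several weeks apart.
- Drop the condition on equivalence. A read that comes before the side-by-side result cannot depend on it, and findings data then exist for every sub-study, including any that do not confirm equivalence.
- Run the side-by-side comparison last.

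No extra scan or injection is needed. The cost is reader time and a longer first session. With two exams per subject and three readers, a sub-study whose diagnostic read would have been skipped adds 33 × 2 × 3 = 198 to 37 × 2 × 3 = 222 reads. At the stated total of 204 subjects the full load is 204 × 2 × 3 = 1,224 reads, which the present plan would also reach if every sub-study confirmed equivalence.

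Recall is reduced, not abolished, because each reader still sees both exams of a patient, though singly and weeks apart.

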After appropriate patient consent and preparation, we will randomize the order in which the patient will receive the Standard of Care PET/CT and the Low Dose PET/CT (i.e. Standard of Care PET/CT on day 1 and Low Dose PET/CT on day 2, or vice versa). If the patient has requested to opt out of the additional whole-body sweep, the patient will be imaged at both examination days at 75 min +/- 10 min post injection. Otherwise, the patient imaging will start with the voluntary whole-body sweep at 60 min +/- 10 min, followed by the standard of care whole-body sweep at 75 min +/- 10 min.

It is well established that the image quality in patients that are classified by the WHO Body Mass Index (BMI) criteria as \Rightarrow obese (BMI \Rightarrow 30) is reduced and that longer bed volume acquisition times improves image quality [JNM Tech 2014 Sanchez-Jurado]. We will therefore increase the otherwise constant acquisition time per bed volume from 90 s to 120 s in those patients for both dose levels.

Using segmented reconstruction, we will be able to down sample the acquisition to be simulated as a 90 s acquisition for overall consistency.

As we are using four different current technology PET/CT systems, we will perform 4 sub-studies that are otherwise fully equivalent.

Sub-Study A: 481 MBq (13 mCi) ¹⁸F-FDG vs. 185 MBq (5 mCi) using Gemini Astonish PET/CT

Sub-Study B: 481 MBq (13 mCi) ¹⁸F-FDG vs. 185 MBq (5 mCi) using Biograph mCT **Sub-Study C:** 481 MBq (13 mCi) ¹⁸F-FDG vs. 185 MBq (5 mCi) using Discovery PET/CT

Sub-Study D: 481 MBq (13 mCi) ¹⁸F-FDG vs. 185 MBq (5 mCi) using Vereos 128 digital PET/CT

We are furthermore planning two additional sub-studies.

Current simulations indicate that we should be able to further reduce the FDG imaging pharmaceutical dose to an even lower level. We will determine that comparison level after completing of Sub-Study D. At this time we would assume that the clinical SOC dose would have been already reduced to 240.5 MBq (6.5 mCi), and we would then compare it to 92.5 MBq (2.5 mCi).

Sub-Study E: 241 MBq (6.5 mCi) ¹⁸F-FDG vs. 93 MBq (2.5 mCi) using Vereos 128 digital PET/CT

We plan for the possibility that one of the three-Sub-Studies (A-B) would not demonstrate equivalency, and we would then perform a modified protocol in which the SOC dosing is compared to a lower and higher dose than originally tested.

Sub-Study F: 481 MBq (13 mCi) ¹⁸F-FDG vs. tbd MBq using the system that did not show equivalency in Sub-Study A-C

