Figure 1 charts the study protocol and randomization.

[figure not shown]

Figure 1: Flowchart of the protocol. After consent, the subject is randomized to the order of low and standard of care dose PET/CT. If the patient opts out of the second whole-body sweep, both exams will be performed at 75 min +/- 10 min p.i., otherwise the 1st sweep will be performed at 60 min +/- 10 min, followed by the 2nd at 75 min +/- 10 min.

Sample Size Considerations

The project statistician has calculated a required sample size of 33 evaluable subjects per imaging modality if we assess tracer uptake (FDG) using both a quantitative (SUVmax) and a visual quality assessment. Based on the literature and our preliminary work, we assume that the coefficient of variation (COV) is 12% and the equivalence limit is 10%. With a total sample size of 33 patients we will achieve 80% power in an equivalence test of means using two one-sided tests (TOST) on data from a two-period cross-over design, using an alpha level of 0.025 (0.05/2) after Bonferroni adjustment each system, respectively. We assume a drop-out rate of 10% (4 subjects) which leads to our target population of 37 enrolled subjects per unique sub-study.

Four imaging systems will be utilized in this study:

- Gemini TOF Astonish system from Philips Healthcare Cleveland
- Biograph mCT from Siemens Knoxville
- Discovery PET/CT from General Electric, Milwaukee
- Vereos 128 PET/CT from Philips Healthcare Cleveland (this is the first commercial digital PET detector system)

The subjects imaged at each of the four PET/CT systems will treated as its own sub-study. Each sub-study will follow the same imaging protocol.

We will evaluate four different state of the art PET/CT system in the above defined six sub-studies which then leads to the overall study population estimate of 204 subjects.

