- Patients unable to lie flat on the scanner for extended periods of time.

Measurement / Instrumentation

Our assessment approaches will be guided by recent community efforts established via the QIBA (RSNA) effort, PET recommendations (SNM), the QIN (NCI) and IROC (NCTN).

In this study, we will not evaluate the impact of the CT-based attenuation scan, as in recent years extensive efforts in CT dose reduction have also translated to substantially lower CT doses for attenuation scans, unless diagnostic read quality is needed to simultaneously replace an additional diagnostic CT scan. We will perform all CT-based attenuation scans at the lowest dose we established for our standard of care PET/CT protocol for each specific PET/CT system.

We currently have four different state of the art PET/CT systems within the OSU Wexner Medical Center. We therefore plan to perform this trial in four separate sub-studies, each being independent for each device, with everything else being standardized. With this unique ability to evaluate the dose and timing impact and to prove equivalency using four distinct platforms in parallel, we will achieve the most meaningful outcome and impact. This will allow us to achieve the desired changes of reducing radiation dose and enabling more flexibility in the imaging time post injection.

The imaging data will be assessed in a fully blinded fashion. Our primary endpoint will be the statistical confirmation that the SUV max measured in the regions of interest (ROI) in the target region will reveal a variation of less than 10%. The project statistician has calculated a required sample size of 37 evaluable subjects per sub-study (See section Statistical Considerations). We will treat each of the four PET/CT system as its own sub-study; however, we will perform each of the first four sub-studies identically other than the manufacturer system-induced differences.

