All paper and electronic data/information will be coded prior to any review or analysis. All paper documents will be stored in a locked file cabinet with limited access in the Department of Radiology at The Ohio State University. All electronic data obtained through PACS or IHIS will be stored in a coded manner on password protected servers with limited access in the Department of Radiology at The Ohio State University. No individual identities will be used in any publications resulting from this study. Officials from examining bodies such as the U.S. Food and Drug Administration or NIH may inspect records pertaining to this study.

Internal Validity

This crossover design is necessary to blind the patient and the technologist to be unbiased during the performance of the imaging, as motion artifacts, positioning, and other aspects can influence image quality to some extent.

Data Analysis

Our primary hypothesis is that the SUVmax will be equivalent between standard of care dosing (13 mCi) and the low dose (5 mCi) in each PET/CT system. The two one-sided tests procedure (TOST) will be used to test the equivalence of SUVmax at 75 min post injection between the standard care of dosing and the low dose. As SUVmax is known to have lognormal distribution, the data will be log-transformed before all analysis. Holm-Bonferroni method will be used to adjust for multiple ROIs. The McNemar-Bowker's test will be used to evaluate the inter-reader reliability in image quality measured from 1-10 scale between every two readers. The average scores will be calculated among those 3 readers. The TOST test will be used to

test the equivalence in the average score of image quality between the standard care of dosing and the low dose.

The percentage of change in SUVmax measured from 60 min to 75 min will be tested first for equivalence between the standard of care dosing and the low dose target ROI in each PET/CT system. Then the SUVmax measured at 60 min will be compared to SUVmax measured at 75 min within standard care of dosing and the low dosing groups, respectively.

V. Bibliography

- 3. Miletich, RS. Positron emission tomography for neurologists. *Neurol Clin.* Feb 2009;27(1):61-88.

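### Holm-Bonferroni over ROIs does not match the one equivalence verdict per PET/CT system; if all ROIs must pass, it only costs power

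*Protocol*

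**What the plan says.** All places are in section IV, Procedures, of the protocol.

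- **Level of the hypothesis (Data Analysis).** "Our primary hypothesis is that the SUVmax will be equivalent between standard of care dosing (13 mCi) and the low dose", and the sentence goes on to say that this applies in each PET/CT system. The test is TOST on log-transformed SUVmax at 75 minutes.
- **Multiplicity (Data Analysis).** "Holm-Bonferroni method will be used to adjust for multiple ROIs". This implies one TOST result per ROI. The number of ROIs is not given.
- **Primary endpoint (Measurement / Instrumentation).** The aim is to confirm that "the SUV max measured in the regions of interest (ROI) in the target region will reveal a variation of less than 10" per cent. The plural wording covers the ROIs together but does not state a success rule.
- **Action on the result (Research Design).** Sub-Study F provides for the case that "one of the three-Sub-Studies (A-B) would not demonstrate equivalency" and is run "using the system that did not show equivalency in Sub-Study A-C". This needs one verdict per system.
- **Sample size (Sample Size Considerations).** "we assume that the coefficient of variation (COV) is 12% and the equivalence limit is 10" per cent. On this basis 33 evaluable subjects are said to give 80% power in a crossover TOST at alpha 0.025. No allowance for several ROIs appears.

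**The concern.** The named procedure answers a different question from the one the trial acts on. Holm is designed for a family of separate claims, each of which may be made by itself. It limits the chance that any one of them is false. The hypothesis and the Sub-Study F decision instead need one statement about a system, and the protocol states no link between the ROI results and that statement.

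The choice of rule matters. In the scenarios below, with three truly equal ROIs, at least one passes in about 89% of trials, while all three pass under Holm in about 56% (correlation 0.5). The same data could therefore send a system to Sub-Study F under one rule and not under the other. On the rule that the endpoint wording favours, the plan also gives up power without gaining any error control that the verdict needs.

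**Working it through.** **Inputs.** From the protocol: CV 12%, equivalence limit 10%, alpha 0.025 for each one-sided test, 33 evaluable subjects, two-period crossover, log scale. Assumed, because the protocol does not give them: 2 to 5 ROIs, correlation 0, 0.5 or 0.8 between ROIs, the same CV in every ROI, Holm applied at a family alpha of 0.025, and limits 0.90 to 1.10 on the ratio scale.

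**Step 1: reproduce the planned figure (one ROI).**
- Within-patient log SD = √ln(1 + 0.12²) = 0.1196. SD of a paired difference = √2 × 0.1196 = 0.1691.
- SE at n = 33: 0.1691/√33 = 0.0294, with 31 degrees of freedom. Limits: ln 0.90 = −0.1054 and ln 1.10 = 0.0953.
- Exact TOST power at true equality: 0.796 for n = 32 and 0.814 for n = 33. So 33 reproduces, and 33/0.9 = 36.7 gives the 37 to be enrolled.
- The figure is therefore the power of a single TOST at 0.025.

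**Step 2: error rate if every ROI must pass.** If a system is not equivalent, at least one ROI lies at or beyond a limit. The verdict then requires that ROI's own TOST to pass, which has probability at most 0.025. No adjustment is needed. In simulation, with one ROI exactly 10% low and the others equal, all ROIs pass unadjusted in about 0.2% to 2% of trials.

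**Step 3: what Holm adds.** For all K ROIs to pass under Holm, the ordered p-values must satisfy p(1) ≤ α/K, p(2) ≤ α/(K−1), …, p(K) ≤ α. Without adjustment only p(K) ≤ α is needed. Holm adds conditions, so it can only lower power. Simulated power at n = 33 with all ROIs truly equal, for correlation 0 / 0.5 / 0.8:

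| ROIs | All pass, unadjusted (%) | All pass, Holm (%) | Loss (points) |
|---|---|---|---|
| 2 | 66 / 69 / 73 | 65 / 67 / 71 | 1.6 / 1.7 / 2.4 |
| 3 | 54 / 59 / 68 | 50 / 56 / 63 | 3.8 / 3.8 / 4.8 |
| 4 | 44 / 52 / 64 | 38 / 46 / 57 | 6.0 / 6.0 / 7.0 |
| 5 | 36 / 46 / 60 | 28 / 38 / 51 | 7.8 / 8.0 / 9.1 |

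The zero-correlation entries can be checked by hand: 0.814² = 0.66 and 0.814³ = 0.54.

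**Step 4: if one passing ROI were enough.** With three ROIs, one truly 15% low and two equal, at least one passes under Holm in 84 / 81 / 74% of trials. That is the chance of calling a non-equivalent system equivalent under such a rule. Holm still does its own job: an ROI exactly at the limit is itself declared equivalent in only 0.6% to 2.1% of trials (2, 3 or 5 ROIs).

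**The case against.** The strongest reply is that this is missing detail. The ROI list and the success rule are often left to the SAP, which is not at hand. That stands for the list and for the rule as such. It does not cover the choice of Holm, which the protocol itself fixes for a hypothesis stated per system.

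A reader might infer that the plan lets a single passing ROI carry a system. The documents do not support that. No section says so, and the endpoint wording leans towards all ROIs. Nor may one picture normal tissue passing while lesions fail: the ROIs are placed in the target region, and no normal-tissue ROI is named.

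A reader might also take the statement "If the lower dose PET/CT examination is determined to be equivalent to the current standard of care, we will change our standard of care" as a decision driven by one ROI result. It stands under Benefits, speaks of the examination as a whole, and is not a statistical rule. The protocol also plans image-quality, confidence and side-by-side readings.

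Finally, it would go too far to call Holm wrong under every reading. It is valid for separate ROI claims. If every ROI must pass, it is conservative rather than misleading. If one named ROI decided, there would be nothing to adjust, although the text speaks of several. These limits stand and are built into the verdict.

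**Conclusion.** The point holds as a mismatch between procedure and decision; no inflated error rate in the plan as written has been shown. If all ROIs must pass, Holm is unnecessary for the system verdict and costs about 2 points of power with 2 ROIs, 4 to 5 with 3, 6 to 7 with 4 and 8 to 9 with 5. If one passing ROI were accepted, Holm would leave the system claim unprotected, with a 74% to 84% chance of a wrong verdict in the three-ROI example.

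These sizes rest on the assumed ROI number, correlation and common CV. The direction does not: Holm can never raise the power of an all-ROI verdict, and that verdict never needs it for error control. The matter is moderate. It touches the primary conclusion and the Sub-Study F trigger, and a short edit before analysis settles it.

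**What to change.** In Data Analysis, replace the Holm sentence with text such as: *A PET/CT system is declared equivalent only if the TOST is passed in every pre-named ROI, each at the alpha allotted to SUVmax. No adjustment over ROIs is made for this verdict. Holm-Bonferroni applies only to separate claims about single ROIs, which do not by themselves establish equivalence of the system.* Refer to this verdict in Research Design as the trigger for Sub-Study F.

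The edit needs a few sentences and no new data. Its cost is candour about power: the 80% at 33 evaluable subjects holds for one ROI. For the all-ROI verdict it is about 66% to 73% with 2 ROIs and 54% to 68% with 3 (correlation 0.8 giving the higher figures). Reaching 80% would take about 37 to 40 evaluable subjects with 2 ROIs, or 39 to 43 with 3. The sponsor should restate the power, enlarge the sub-studies, or keep the ROI list short. Because enrolment spans varied diseases, the ROIs should be defined so that every patient can contribute to each one; otherwise the number per ROI falls below 33. Naming one primary ROI is a workable alternative and would keep the planned sample size.
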